and thus inform future public health responses, including decisions on implementation and lifting of social distancing measures. Repeating this serosurvey at two time points during the pandemic will allow for the evolution of the pandemic in Ireland to be described.

3. To conduct repeat sampling and symptom questionnaires on the subset of the study population who are antibody positive, and who agree to repeat sampling, in order to understand the kinetics of antibody titres/serological markers over time.

Objectives

The study objectives are:

- To measure the prevalence of antibodies to SARS-CoV-2 in a representative sample of the Irish population in two geographically defined areas
- To estimate the age-specific susceptibility to SARS-CoV-2 infection in the population, in order to inform future vaccination policy
- To compare the prevalence of antibodies to SARS-CoV-2 across two geographical areas with high and low incidence of cases of COVID-19 in Ireland, as defined at the time of commencing the study
- To perform the cross-sectional serosurvey at three time points during the pandemic and document the changing patterns in the prevalence of antibody positivity
- To use the data from the repeated serosurveys to inform models predicting the spread of SARS-CoV-2 infection and the impact of social distancing and other control measures
- To examine the relationship between the presence of antibodies to SARS-CoV-2 and the self-reporting of symptoms consistent with COVID-19 or having a previous diagnosis of COVID-19
- For those participants who have antibodies to SARS-CoV-2, to measure serial samples for antibody titres and antibody function over time

Study Design

There are 2 components to the study:

- A cross-sectional prospective study of the Irish population in two geographic areas which will be repeated twice over time in different areas, as determined by the evolution of the pandemic and other logistical factors. For each cross-sectional survey, areas of higher incidence and lower incidence will be chosen. The study will be adapted from the WHO protocol, 'Population-based age-stratified sero-epidemiological investigation protocol for COVID-19 virus infection', to suit the Irish context.
- A serial sampling study among the subset of participants who are antibody positive, if they consent to serial sampling at 3 months, 6 months and 12 months. At the time of each sample, they will be asked to complete a symptom questionnaire.

Sampling procedure

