Separate consent will be obtained, from participants who have antibodies to SARS-CoV-2 detected, and who agree to take part in the second study for data collection and processing, at 3, 6 and 12 months, for sample storage for 2 years, and for international sharing of the data with WHO (in an anonymised format)

Sample collection and processing

Sample testing locations will be established by the HSE in the two selected areas where the study is being undertaken. Options for suitable sites are currently under investigation. The sites will not be centres currently used for testing patients for possible current COVID-19 infection.

On arrival at the test centre, the team (administrative personnel and nurse phlebotomists) will confirm that the person is registered as a participant in the study, and will obtain written consent for sampling. Demographic details will be confirmed. A venous serum sample of 10mls will be collected

from each person by the nurse phlebotomist. Arrangements will be made for the participant to receive reimbursement for travel expenses incurred.

Specimens will be transported to the National Virus Reference Laboratory (NVRL) at 4 degrees Centigrade for testing using registered couriers. Consent forms will be sent to HSE HPSC where they will be scanned and entered into the secure database. The paper copies will then be securely shredded.

Those participants with detectable antibody to SARS-CoV-2 will also be invited to take part in a follow up study to determine if these antibodies are persistent 3, 6 and 12 months after the initial samples were taken and if they developed symptoms consistent with COVID-19 during this time. They will be asked for consent to take part in this study when results of the first round of testing are available. They will not be provided with the results of these further tests.

Laboratory testing

The SARS-CoV-2 IgG assay to be used by the NVRL will be selected based upon the antigenic targets utilised in the test, review of data generated by the manufacturer and independent assay assessment and also assay verification performed at the NVRL. It is probable, based upon the anticipated numbers for testing, that an automated platform will be used.

The format for the current assays is not suitable for the accurate investigation of SARS-CoV-2 IgG in samples collected “non-invasively” such as oral fluid. However, if a suitable test is identified this approach will be considered and a study amendment will be sought.

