Individual results of the blood test will be provided to participants by letter, explaining that the result is not a diagnostic test, and is meaningful at a population rather than individual level. They will be advised that the presence of antibodies may not equate to immunity from future SARS-CoV-2 infection as further research is required to enhance our understanding of this disease, including the extent to which prior infection confers immunity. They will be advised to continue to follow all social distancing and hygiene measures recommended by the government

The potential benefits and harms of providing feedback to individuals were weighed up and on balance it was felt that feedback on presence of Ab to SARS-CoV-2 was appropriate as it would provide the person with knowledge that they had been infected and that it would be carefully explained to the person that the implications of that finding for re-infection was uncertain at this time. Participants will also be given the 'right not to know' and can specify at time of providing consent to participate to not receive their results.

Participants will be advised that they may phone a public health doctor member of the study team if they have queries about the result and will be provided with a contact phone number.

The participant's GP will also be provided with the result, if the participant has agreed to this.

Anonymised results will be shared with NPHE to inform the national pandemic response. In the interests of openness and transparency, a report on the study results will also be shared with the general public, via the HSE and HSE HPSC websites.

The HSE HPSC, through its role as IHR focal point for Ireland, will also share anonymised results with the World Health Organization (WHO) to add to global knowledge on the spread of COVID-19.

A manuscript outlining the study methodology, the results and their interpretation will be submitted for publication in a peer reviewed scientific journal

Those participants with detectable antibody to SARS-CoV-2 will also be invited to take part in a follow up study to determine if these antibodies are persistent 3, 6 and 12 months after the initial samples were taken and if they developed symptoms consistent with COVID-19 during this time. They will be asked for consent to take part in this study when results of the first round of testing are available. They will not be provided with the results of these further tests.

Repeat cross sectional survey

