This cross-sectional survey will be repeated twice during the pandemic, with a different sample of participants, from high and low incidence areas. The interval will be determined by the evolution of the pandemic and other logistical factors.

Oversight

A steering group has been established to oversee the design and operation of the study. The membership and terms of reference are set out in Appendix A.

Data processing and safeguards

Using the PCRS database, the HSE HPSC will write to randomly selected individuals, seeking their participation in the study. Those who are interested in participating will be asked to contact the research team at HSE HPSC to indicate their consent to participate and to seek further information if required.

For those who contact the research team, and who give initial verbal consent to participate in the study, information on name, address, sex, age/date of birth, occupation, GP details, and history of symptoms consistent with COVID-19 or a previous diagnosis of COVID-19 will be gathered by phone. This information will be entered and stored in a secure database at HSE HPSC.

Appointments for testing at HSE centres will be organised using the online swiftqueue system. Patients will be allocated a unique study ID. At the testing centres, the staff will have the names, date of birth and study ID numbers of the consenting participants. This information is needed for correctly identifying participants, for the testing procedure and for labelling the serum samples.

The samples, containing the name, date of birth and unique study ID number, and accompanying form containing the same ID, name and date of birth will be sent to NVRL via registered courier.

At NVRL the samples will be processed using the unique study ID, name and date of birth.

NVRL will provide the serology result to HSE HPSC for entry into the secure database using name, date of birth and unique study ID number. If the participant has given consent to receive their test result, the result, and an explanation of how it should be interpreted, will be provided to the participant by letter from HSE on behalf of the study partners. They will also be provided with contact details if they wish to discuss this further with a public health doctor from the research team.

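### The follow-up invitation goes only to antibody-positive participants, with no exception for those who declined their result, so it would reveal a positive result to them

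*Protocol*

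**What the plan says.** Four statements in the protocol bear on this.

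- **The right to decline the result.** Under Reporting of the results, participants "can specify at time of providing consent to participate to not receive their results". The same section says that the benefits and harms of individual feedback were weighed, so the opt-out is a deliberate protection.
- **Where that right takes effect.** Data processing and safeguards applies it to the result letter. The sentence on that letter begins "If the participant has given consent to receive their test result".
- **Who is invited to follow-up, and when.** Sample collection and processing and Reporting of the results carry the same sentence: "Those participants with detectable antibody to SARS-CoV-2 will also be invited to take part in a follow up study". Both add: "They will be asked for consent to take part in this study when results of the first round of testing are available".
- **What the follow-up study is.** Study Design describes it as "A serial sampling study among the subset of participants who are antibody positive, if they consent to serial sampling". Informed consent says: "Separate consent will be obtained, from participants who have antibodies to SARS-CoV-2 detected". Its stated purpose is "to determine if these antibodies are persistent 3, 6 and 12 months after the initial samples were taken".

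**The concern.** The opt-out controls one channel, the result letter. The follow-up invitation is a second channel that carries the same information, and nothing in the protocol text closes it for people who opted out. Staff who follow the invitation rule literally would tell an opted-out person that antibodies were found. That is the information the opt-out exists to withhold, and it cannot be taken back once given.

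There is a smaller statistical consequence. If staff deal with the problem informally by leaving opted-out positives uninvited, the serial cohort becomes the positives who accepted contact. The protocol does not define the cohort that way and does not plan to report how many positives were left out. Data analysis calculates persistence of antibodies among those included in the serial study, so a reader would need that count to judge whom the proportions describe.

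**Working it through.** There is no figure in the plan to reproduce. The check sets the rules side by side.

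1. **Condition for an invitation.** A person is invited only if antibody is detected (Study Design, Informed consent, Sample collection and processing, Reporting of the results). No antibody-negative participants are invited, so nothing masks the meaning of an invitation.
2. **Timing.** The approach is made once results are available. It is therefore conditional on a known positive result.
3. **Content.** The purpose is to see whether the antibodies already found persist. Someone asked to consent to that study cannot be told its purpose without learning that antibodies were found.
4. **Search for an exception.** Informed consent lists consent for sampling, data processing, sharing with WHO and storage. It contains no question at first consent about later contact if positive. Neither invitation sentence mentions the opt-out. The statement that results of the further tests will be withheld covers only the later samples, so it does not protect the first result.
5. **Outcome in each case, with the text applied literally:**

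| Choice at consent | First result | Result letter | Invitation | What the participant learns |
|---|---|---|---|---|
| Accepts result | Positive | Yes | Yes | Positive, from the letter |
| Accepts result | Negative | Yes | No | Negative, from the letter |
| Declines result | Positive | No | Yes | Positive, from the invitation |
| Declines result | Negative | No | No | Nothing directly |

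The third row is the defect: the letter is withheld as promised and the invitation discloses the result anyway.

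6. **Size.** At full recruitment the first survey tests 1,000 + 1,600 = 2,600 people (Sample size). The expected number in the third row is 2,600 × p × q, where p is the proportion with detectable antibody and q is the proportion of those who declined their result. The protocol gives neither p nor q, so no number follows. Later surveys use areas not yet chosen, which leaves p still more open there.

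**The case against.** The strongest reply is that one unstated exception removes the problem. The result letter already depends on the participant's choice; apply the same condition to the invitation and both rules are kept. The invitation sentences do not say that every positive must be approached, and the wording of the invitation is not given. The consent form and information leaflet, where a re-contact question or a warning would naturally sit, are not in the text reviewed. Much of this stands, and it rules out several stronger readings that a reader might infer.

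- *That the two rules cannot be reconciled.* They can, by a single conditional clause. The point is that the clause is absent from both places where the invitation rule is stated.
- *That the study is shown to break its promise to participants.* That depends on what they are told and asked at consent, which cannot be seen here. What can be shown is that the protocol text, followed literally, discloses the result.
- *That leaving out opted-out positives would select the serial cohort after results are known, with no record.* The documents point the other way. The choice is made at consent, and written consent precedes blood sampling. Consent forms are scanned and kept, serology results enter the same database, and the choice must be known in order to send letters. The count should be recoverable; it is simply not planned to be reported.
- *That receiving no invitation discloses a negative result.* This holds only for someone who knows the invitation rule and its timing, and the visible text does not say what participants are told about that at baseline.
- *That a definite number of people is affected.* Any such figure needs a seroprevalence and an opt-out rate that the protocol does not contain.

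What the reply does not answer is that the invitation rule is stated twice without the needed condition. A safeguard in the consent form would still contradict those sentences until they were amended.

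**Conclusion.** The point holds in a limited form. The protocol grants a right to decline the result, applies it to the result letter, and then states an invitation rule that discloses a positive result to anyone who used that right and tested positive. For each such person who is invited, disclosure follows from the text. How many there would be is unknown.

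The conclusion assumes that the invitation rule is applied as written and that the invitation conveys the purpose of the follow-up study. It does not depend on any prevalence or opt-out figure. The seroprevalence estimates and the cross-sectional design are untouched, and no bias in the persistence proportions has been shown. It should be corrected, because one stated rule defeats another stated protection and the remedy is cheap.

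**What to change.** 1. **Baseline written consent.** Before any result is known, add a question of this kind: 'If antibodies are found in your sample, may we contact you about giving repeat samples? Being contacted would tell you that your result was positive.' Because the question makes the rule known, it could add that someone who agrees and is not contacted may infer a negative result. A person who wishes to learn nothing can then answer no.
2. **Protocol text.** Amend the invitation sentence in both Sample collection and processing and Reporting of the results so that only positives who agreed at baseline are invited. The separate follow-up consent stays as it is. Check that the consent form and leaflet say the same.
3. **Reporting.** When describing the serial cohort, split all positives into those not approached because of their baseline answer, those approached who declined, and those enrolled.

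The cost is one consent question, a conditional clause in two places and one line of accounting. The Ethics section says the proposal is being submitted for approval, so the change can be made before anyone is enrolled. The downside is that a few positives are lost to follow-up.
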